**Table 5. APR-548 dose management guidelines for nausea, vomiting, and/or diarrhea adverse events**

Worst toxicity grade	Dose modification guidelines for APR-548 *
Grade 1	
 
Maintain dose level of APR-548 and monitor subject; provide supportive care measures as clinically indicated.
 

Grade 2	
 
Interrupt APR-548 dosing and monitor subject; treat promptly.
 
Resume at current dose level if toxicity resolves to Grade <math>\leq</math> 1 or baseline, with or without use of supportive care measures, within 72 hours of onset.
 
If toxicity does not resolve to Grade <math>\leq</math> 1 within 72 hours despite maximal medical intervention(s), then reduce APR-548 by 1 dose level once the toxicity resolves to
 

		
Grade ≤1 or baseline.
 
 
• If unable to reduce APR-548 dose, discuss with study Medical Monitor before resuming or discontinuing treatment.
 
• For subsequent doses of APR-548, pre-medication with prophylactic supportive therapy should be given if clinically indicated.
 

Grade 3	1 st occurrence	
 
• Interrupt APR-548 dosing and monitor subject; treat promptly.
 
• Resume at current dose level if toxicity resolves to Grade ≤1 or baseline, with supportive care measures, within 72 hours of onset.
 
• If toxicity does not resolve to Grade ≤1 within 72 hours despite maximal medical intervention(s), then reduce APR-548 by 1 dose level once the toxicity resolves to Grade ≤1 or baseline.
 
• If unable to reduce APR-548 dose, discuss with study Medical Monitor before resuming or discontinuing treatment.
 
• For subsequent doses of APR-548, pre-medication with prophylactic supportive therapy should be given.
 

	2 nd occurrence	
 
• Interrupt APR-548 dosing and monitor subject; treat promptly.
 
• Reduce APR-548 by 1 dose level if the toxicity resolves to Grade ≤1 or baseline within 72 hours of onset.
 
• If toxicity does not resolve to Grade ≤1 despite maximal medical intervention(s) within 72 hours of onset, then consult with study Medical Monitor before resuming or discontinuing APR-548.
 
• If unable to reduce APR-548 dose, discuss with study Medical Monitor before resuming or discontinuing treatment.
 
• Prior to subsequent doses of APR-548, reassess prophylactic supportive therapy regimen and adjust as clinically indicated.
 

	3 rd occurrence	
 
• Interrupt APR-548 dosing and monitor subject; treat promptly.
 
• Consult with study Medical Monitor before resuming or discontinuing APR-548.
 

Grade 4	
 
• Interrupt APR-548 dosing and monitor subject; treat promptly.
 
• Consult with study Medical Monitor before resuming or discontinuing APR-548.
 
	

\* Refer to Section [5.3.5](#) for details on supportive management guidelines specific to nausea, vomiting, and/or diarrhea.

**Table 6. Dose management guidelines for APR-548 and azacitidine for worsening neutropenia from baseline with or without fever**

Toxicity	Occurrence	APR-548	Azacitidine
Grade 3 or 4 neutropenic fever or Worsening neutropenia from baseline to Grade 4 without fever	1 st occurrence	
 
• Interrupt dosing and monitor subject; treat promptly.
 
• Resume at current dose level if neutropenia and fever (if present) resolve to baseline within 7 days after onset.
 
• If toxicity does not resolve to baseline despite maximal medical intervention(s) within 7 days of onset, then reduce APR-548 by 1 dose level once the toxicity resolves to baseline.
 
• If unable to reduce APR-548 dose, discuss with study Medical Monitor before resuming or
 
	Follow dose modification guidelines per USPI  .

		
discontinuing treatment.
 
 
Initiate or reassess prophylaxis measures. Refer to Sections 5.3.3 and 5.3.4 for supportive management guidelines specific to infection prophylaxis and neutropenia, respectively.
 
	
	2 nd occurrence	
 
Hold all study treatments and monitor subject; treat promptly.
 
Assess current infection prophylaxis measures being administered and adjust treatment plan as clinically indicated. Refer to Sections 5.3.3 and 5.3.4 for supportive management guidelines specific to infection prophylaxis and neutropenia, respectively.
 
While APR-548 and azacitidine are interrupted, consult with study Medical Monitor before resuming or discontinuing study treatments.
 
	

**Table 7. Management of ocular-associated adverse events**

Parameter	Worst toxicity	Occurrence	Dose Modifications for APR-548
Retinopathy and optic nerve disorders	Grade 1	1 st occurrence	Interrupt treatment with APR-548. Monitor and treat patient promptly as clinically indicated. Consult with study medical monitor before resuming dosing of APR-548 at same dose level once event has stabilized or resolved to baseline.
		2 nd occurrence	Interrupt treatment with APR-548. Monitor and treat patient promptly as clinically indicated. Consult with study medical monitor to determine if patient should resume at same dose level or if APR-548 should be reduced by 1 dose level.
		3 rd occurrence	Interrupt treatment with APR-548. Monitor and treat patient promptly as clinically indicated. Consult with study medical monitor to determine if APR-548 treatment should be reduced by one dose level or permanently discontinued.
	Grade 2	1 st occurrence	Interrupt treatment with APR-548. Monitor and treat patient promptly as clinically indicated. Notify medical monitor and report as SAE (AESI). Once resolved to baseline parameters, then reduce dose of APR-548 by one level. If unable to reduce dose of APR-548, discuss with study medical monitor before resuming or discontinuing treatment with APR-548.
		2 nd occurrence	Permanently discontinue treatment with APR-548. Monitor and treat patient promptly as clinically indicated. Notify medical monitor and report as SAE (AESI).
	≥Grade 3	N/A	Permanently discontinue subject from APR-548.
	Other	Grade 1	Interrupt treatment with APR-548 for new finding or worsening from baseline. Monitor and treat patient promptly as clinically indicated. May resume at current dose level once stabilized or resolved to baseline. Consult with study medical monitor before resuming or reducing dose of APR-548 for a second or greater occurrence of same event.
	Grade 2	1 st occurrence	Interrupt treatment with APR-548 for new finding or worsening from baseline. Monitor and treat patient promptly as clinically indicated. Notify Medical Monitor and report as SAE (AESI).

		Once resolved to baseline parameters, then: First occurrence, reduce dose of APR-548 by one level. If unable to reduce dose of APR-548, discuss with study medical monitor before resuming or discontinuing treatment with APR-548.
	2 nd occurrence	Permanently discontinue treatment with APR-548. Monitor and treat patient promptly as clinically indicated. Notify Medical Monitor and report as SAE (AESI).
≥Grade 3	N/A	Permanently discontinue subject from APR-548.

**Table 8. Management of CNS adverse events (e.g., dizziness, tremor, confusion, and ataxia)**

Worst toxicity	Dose Modifications for APR-548
Grade 1	Maintain dose level
Grade 2	If resolved to ≤Grade 1 with medical therapy, continue same dose level If not resolved despite treatment interruption and maximal medical therapy, interrupt treatment with APR-548 and contact the study Medical Monitor.
Grade ≥3	Interrupt treatment with APR-548 and give medical therapy. If resolved (to ≤Grade 1) with medical therapy, reduce APR-548 by one dose level when treatment is restarted. If not resolved despite treatment interruption and maximal medical therapy, consult study Medical Monitor to determine if a reduction of APR-548 by one dose level could be undertaken once the CNS AE resolves to ≤Grade 1 or if APR-548 should be permanently discontinued.
Grade 4	Permanently discontinue subject from APR-548.

**Table 9. Management of serum creatinine elevations and acute kidney injury**

Parameter	Worst toxicity †	Occurrence	Dose Modifications for APR-548
Serum Creatinine Elevations	Grade 1 (<1.5 × baseline)	N/A	Maintain dose level of APR-548
	Grade 2 (>1.5 to 3.0 × baseline)	1 st occurrence	Omit dose until resolved to ≤Grade 1 or baseline, then maintain dose level. Monitor subject.
		2 nd occurrence	Reduce by 1 dose level. If unable to reduce by 1 dose level, consult with study Medical Monitor before resuming or discontinuing study treatment.
	Grade 3 (>3.0 – 6.0 × baseline)	1 st occurrence	Interrupt dosing with APR-548 and monitor subject. Treat promptly. Reduce by 1 dose level. If event resolved to ≤Grade 1 or baseline less than 7 days from onset. If unable to reduce by 1 dose level, consult with study Medical Monitor before resuming or discontinuing study treatment. If not resolved or resolved in >7 days, evaluate if other contributing factors are present. If none, or after consideration of best interest of the subject, discontinue subject from APR-548. If other factors present, consider continuing after ↓ 1 dose level.
		2 nd occurrence	Permanently discontinue treatment with APR-548.
	Grade 4 (>6.0 × baseline)	N/A	Permanently discontinue subject from APR-548.
Acute kidney injury (including acute tubular necrosis)	≤Grade 2	1 st occurrence	Omit dose until resolved to ≤Grade 1 with medical therapy. Consult with study Medical Monitor to discuss if a dose reduction should be undertaken.
		2 nd occurrence	Permanently discontinue treatment with APR-548.
	Grade 3	1 st occurrence	Omit dose until resolved to ≤Grade 1 with medical therapy. Consult with study Medical Monitor to determine if dose reduction or permanent discontinuation of APR-548 should be undertaken.
		2 nd occurrence	Permanently discontinue treatment with APR-548.
	Grade 4	N/A	Permanently discontinue subject from APR-548

†Common Terminology Criteria for Adverse Events (CTCAE) version 5.

\* If dose reduction by 1 dose level is not available, consultation with study Medical Monitor should occur prior to resuming treatment with APR-548.

**Table 10. Management of liver enzymes elevation**

Parameter	Worst toxicity	Occurrence	Dose Modifications for APR-548
Bilirubin ‡	Grade 1 (>ULN - 1.5 × ULN)	N/A	Maintain dose level with liver function tests (LFTs) ‡ monitored as per protocol
	Grade 2 (>1.5 - 3.0 × ULN) with ALT or AST ≤3.0 × ULN	1 st occurrence	Omit dose until resolved to ≤Grade 1 or baseline, then: If resolved in ≤7 days, maintain dose level. If resolved in >7 days, then ↓ 1 dose level. If unable to reduce by 1 dose level, then consult with study Medical Monitor before resuming or discontinuing study treatment.
		2 nd occurrence	Omit dose until resolved to ≤Grade 1 or baseline, then ↓ 1 dose level. If unable to reduce by 1 dose level, then consult with study Medical Monitor before resuming or discontinuing study treatment.
	Grade 3 (>3.0 - 10.0 × ULN) with ALT or AST ≤3.0 × ULN	1 st occurrence	Omit dose until resolved to ≤Grade 1 or baseline, then: If resolved in ≤7 days, ↓ 1 dose level. If no subsequent event, consider re-escalation to original dose level after consultation with study Medical Monitor. Omit dose until resolved to ≤Grade 1, then: ↓ 1 dose level. If not resolved or resolved in ≤7 days, evaluate if other contributing factors are present. If none, or after consideration of best interest of the subject, discontinue subject from APR-548.
		2 nd occurrence	Evaluate if other contributing factors are present. If none, or after consideration of best interest of the subject, discontinue subject from APR-548. If other factors present, consider continuing after ↓ 1 dose level. If unable to reduce by 1 dose level, then consult with study medical monitor before resuming or discontinuing study treatment.
	Grade 4 (>10.0 × ULN)	N/A	Permanently discontinue subject from APR-548
AST or ALT	Grade 1 (>ULN - 3.0 × ULN if baseline was normal; 1.5 - 3.0 × baseline if baseline was abnormal)	N/A	Maintain dose level with LFTs ‡ monitored per protocol
	Grade 2 (>3.0 - 5.0 × ULN if baseline was normal; >3.0 - 5.0 × baseline if baseline was abnormal) in the absence of total bilirubin	1 st occurrence	Omit dose until resolved to ≤Grade 1 or baseline, then, if resolved in ≤7 days, maintain dose level. If resolved in >7 days, then ↓ 1 dose level. If unable to reduce by 1 dose level, then consult with study Medical Monitor before resuming or discontinuing study treatment
		2 nd occurrence	Omit dose until resolved to ≤Grade 1 or baseline, then ↓ 1 dose level. If unable to reduce by 1 dose level, then consult with study Medical Monitor before resuming or discontinuing study treatment.

Parameter	Worst toxicity	Occurrence	Dose Modifications for APR-548
	elevation to $> 2.0 \times \text{ULN}$		
	Grade 3 ( $> 5.0 - 20.0 \times \text{ULN}$ if baseline was normal; $> 5.0 - 20.0 \times \text{baseline}$ if baseline was abnormal) in the absence of total bilirubin elevation to $> 2.0 \times \text{ULN}$	1 st occurrence	Omit dose until resolved to $\leq \text{Grade 1}$ or baseline. For 1 st occurrence, if resolved in $\leq 7$ days, then maintain dose level. If not resolved or resolved in $< 7$ days, evaluate if other contributing factors are present. If none, or after consideration of best interest of the subject, discontinue subject from APR-548. If other factors present, consider continuing after $\downarrow 1$ dose level. If unable to reduce by 1 dose level, then consult with study Medical Monitor before resuming or discontinuing study treatment.
		2 nd occurrence	Evaluate if other contributing factors are present. If none, or after consideration of best interest of the subject, discontinue subject from APR-548. If other factors present, consider continuing after $\downarrow 1$ dose level. If unable to reduce by 1 dose level, then consult with study Medical Monitor before resuming or discontinuing study treatment.
	Grade 4 ( $> 20.0 \times \text{ULN}$ if baseline was normal; $> 20.0 \times \text{baseline}$ if baseline was abnormal)	N/A	Permanently discontinue subject from APR-548

◊ Please note that the Investigator is responsible for determining whether a subject meets potential Hy's Law criteria at any point during the study. Hy's law identifies subjects at risk for severe drug-induced liver injury and is defined as AST or ALT  $\geq 3 \times \text{ULN}$  together with Total Bilirubin Level  $\geq 2 \times \text{ULN}$ , where no other reason, other than the suspected drug, can be found to explain the combination of increases, e.g., elevated alkaline phosphatase indicating cholestasis, viral hepatitis, or another drug. APR-548 should be permanently discontinued in any subject who meets potential Hy's Law criteria.

† Common Terminology Criteria for Adverse Events (CTCAE) version 5.

‡ For subjects with Gilbert's syndrome, these dose modifications apply to changes in direct bilirubin only.

\* LFTs include albumin, ALT, AST, total bilirubin (fractionated if total bilirubin  $> 2.0 \times \text{ULN}$ ), alkaline phosphatase.

[figure not shown]

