#### **4.7 Inclusion Criteria**

1. Provision of signed and dated, written informed consent prior to any study specific procedures.
2. Documented diagnosis of *TP53*-mutant MDS, according to WHO criteria that is previously untreated and meets IPSS-R classification of intermediate, high, or very high risk disease, or *TP53*-mutant MDS that is relapsed and/or refractory to prior treatments. Eligible *TP53* mutations are defined in [Appendix VII](#).
3. Adequate organ function as defined by the following laboratory values:
  - a. Creatinine clearance  $\geq 60$  mL/min (by Cockcroft-Gault method, [Appendix I](#)),
  - b. Total serum bilirubin  $\leq 1.5 \times$  upper limit of normal (ULN), unless due to Gilbert's syndrome or MDS organ involvement,
  - c. Alanine aminotransferase (ALT) and aspartate aminotransferase (AST)  $\leq 2.5 \times$  ULN, unless due to MDS organ involvement.
4. Age  $\geq 18$  years at the time of signing the informed consent form.
5. Eastern Cooperative Oncology Group (ECOG) performance status of 0, 1 or 2 ([Appendix II](#)).
6. Projected life expectancy of  $\geq 12$  weeks.
7. Clear ocular media and adequate pupil dilation to permit fundus examination and retinal imaging.
8. Female subjects must be surgically sterile, postmenopausal (for at least 1 year), or have negative results for a pregnancy test at screening, on a serum or urine sample obtained within 7 days prior to initiation of study treatment.
9. Heterosexual female subjects of childbearing potential must agree to use adequate contraception or practice sexual abstinence as the preferred and usual lifestyle of the subject during the study and for up to 90 days after study treatment discontinuation. Adequate contraception is defined by the concomitant use of 2 effective methods of contraception, which can be comprised of two barrier methods, or a barrier method plus a hormonal method or an intrauterine device that meets  $<1\%$  failure rate for protection from pregnancy in the product label ([Appendix III](#)). Females of non-childbearing potential are those who are postmenopausal greater than 1 year or who have had a bilateral tubal ligation or hysterectomy or bilateral oophorectomy. Female subjects must refrain from egg cell donation while on study treatment and for at least 90 days after the last dose of APR-548 or azacitidine, whichever is longer.

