## 5.2 Dose Interruptions/Withholding

Study treatment, including APR-548 and azacitidine, may be withheld from a subject in the event of intercurrent illness, TEAE, administrative reasons, or other reasons. If the subject's condition subsequently improves, or the situation that resulted in withholding study drug resolves, the investigator may resume dosing as soon as possible, unless the reason for dose interruption falls into one of the categories noted below.

Dosing with APR-548 may be permanently discontinued in any subject who develops any retinopathy or optic nerve disorder (of  $\geq$ Grade 2), regardless of perceived attribution to study drug, and if a clinical retina specialist or ophthalmologist determines a retinal or optic nerve finding is substantially and clinically significantly changed from the subject's baseline test, and that continued participation in the trial would increase the risk for such a finding to worsen (see [Table 7](#) for details).

Dose management guidelines in [Table 2](#) or [Table 3](#) should be followed for each occurrence of a  $\geq$ Grade 3 hematologic or non-hematologic toxicity where relationship to APR-548 and/or azacitidine cannot be excluded (e.g., due to underlying disease).

Dose management guidelines in [Table 4](#), [Table 5](#) and [Table 6](#), respectively, should be followed for each occurrence of infections, nausea/vomiting/diarrhea, and neutropenia with and without fever.

Dose management guidelines in [Table 8](#), [Table 9](#) and [Table 10](#), respectively, should be followed for each occurrence of CNS-associated TEAEs, renal TEAEs (serum creatinine elevations or acute kidney injury), or hepatic TEAEs (elevations in bilirubin, ALT and/or AST).

Subjects experiencing  $\geq$ 2 occurrences of the same TEAE where attribution to APR-548 and/or azacitidine cannot be excluded (e.g., due to underlying disease), the investigator should consult with the study Medical Monitor before study treatments are resumed or discontinued.

Treatment may be discontinued if a TEAE has not improved ( $\leq$ Grade 1 or baseline level) or resolved after  $\leq$ 4 weeks. Consult with the study Medical Monitor to discuss the subject's condition before permanently discontinuing study treatment.

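### Table 10 has no required hold for bilirubin >1.5 to <2.0 × ULN when both enzymes exceed 3.0 × ULN but stay within 3.0 × an abnormal baseline

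*Combined protocol and SAP*

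**What the plan says.** Section 5.2 directs sites to Table 10 for hepatic TEAEs. The parts of Table 10 that matter here are:

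- **Bilirubin, Grade 2.** The row is headed "Grade 2 (>1.5 - 3.0 × ULN) with ALT or AST ≤3.0 × ULN". At first occurrence the dose is omitted until recovery to Grade 1 or baseline. If recovery is slow, "If resolved in >7 days, then ↓ 1 dose level". The Grade 3 bilirubin row carries the same enzyme condition. The Grade 1 row stops at 1.5 × ULN.
- **AST/ALT, Grade 1.** The range includes "1.5 - 3.0 × baseline if baseline was abnormal", with no bilirubin condition. The action begins "Maintain dose level with LFTs".
- **AST/ALT, Grade 2 and above.** For an abnormal baseline, omission starts only above 3.0 × baseline.
- **Hy's Law footnote.** It needs AST or ALT ≥3 × ULN together with total bilirubin ≥2 × ULN, "where no other reason, other than the suspected drug, can be found to explain the combination of increases". It then states that "APR-548 should be permanently discontinued in any subject who meets potential Hy's Law criteria".

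Section 4.7 admits subjects with ALT and AST up to 2.5 × ULN, and higher "unless due to MDS organ involvement". Abnormal baselines are therefore expected in the trial.

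**The concern.** The bilirubin row is switched off by an enzyme limit in ULN units, while the enzyme rows that should take over are graded against baseline. For a subject with abnormal entry enzymes, both enzymes can pass 3.0 × ULN, which removes the bilirubin row, long before they pass 3.0 × baseline, which brings in an enzyme row that requires omission. Between those points a Grade 2 bilirubin has no required action. Read as printed, the required action weakens as the enzymes rise in ULN terms.

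The two instructions lead to different conduct in two situations. If the abnormality is still present at the next Day 1, the bilirubin row withholds APR-548. If it took more than 7 days to resolve, the bilirubin row lowers the dose by one level. The maintain instruction does neither. This is a first-in-human study, so a liver rule that can be met only by maintaining the dose, or by nothing, deserves correction.

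**Working it through.** **Inputs.** Let x be the current value of both enzymes and b their common baseline, both in × ULN, with b > 1. Baseline is taken as the entry value. Bilirubin is 1.8 × ULN, inside the band >1.5 to <2.0. The row limits are those of Table 10, and the entry limit of 2.5 × ULN is from Section 4.7.

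**Row conditions**

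1. The bilirubin Grade 2 row needs ALT or AST ≤3.0. It is not met when both are above 3.0.
2. AST/ALT Grade 1 (maintain) is met when 1.5b ≤ x ≤ 3.0b.
3. The AST/ALT omission rows start at x > 3.0b.
4. The Hy's Law footnote needs bilirubin ≥2.0, so it is not met.

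From these:

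- Maintain is the only row met from the larger of 3.0 (exclusive) and 1.5b up to 3.0b.
- No row is met for 3.0 < x < 1.5b, which is possible only if b > 2.0.

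| b | 1.5b | 3.0b | No row | Maintain only |
|---|---|---|---|---|
| 1.2 | 1.80 | 3.6 | none | >3.0 to 3.6 |
| 1.5 | 2.25 | 4.5 | none | >3.0 to 4.5 |
| 2.0 | 3.00 | 6.0 | none | >3.0 to 6.0 |
| 2.5 | 3.75 | 7.5 | >3.0 to <3.75 | 3.75 to 7.5 |
| 4.0 (assumed; needs the organ-involvement exemption) | 6.00 | 12.0 | >3.0 to <6.0 | 6.0 to 12.0 |

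**Cases at bilirubin 1.8 × ULN**

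| Baseline ALT, AST | Now | Ratio to baseline | Row met |
|---|---|---|---|
| 0.8, 0.8 | 0.8, 0.8 | – | bilirubin Grade 2: omit |
| 2.0, 2.0 | 3.5, 3.5 | 3.5/2.0 = 1.75 | maintain only |
| 2.5, 2.5 | 3.5, 3.5 | 3.5/2.5 = 1.4 | none |
| 1.2, 1.2 | 4.0, 4.0 | 4.0/1.2 = 3.33 | enzyme Grade 2: omit |
| 0.8, 0.8 | 4.0, 4.0 | graded on ULN | enzyme Grade 2: omit |
| 2.0, 0.9 | 4.0, 4.0 | 2.0; second graded on ULN | maintain and omit |

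The last three rows mark the edge of the gap. A normal baseline, a rise above 3.0 × baseline, or one enzyme with a normal baseline that is now above 3.0 × ULN each brings in a row that requires omission.

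**Sensitivity to wording.** Because both enzymes are above 3.0, it does not matter whether the enzyme condition means either or both. Because bilirubin is below 2.0, it does not matter how potential Hy's Law is read or whether another cause is found. The windows are the same under all 2 × 2 × 2 = 8 combinations.

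**Other rules that might fill the gap.** Table 3 covers Grade 3 or 4 and sends hepatic events back to Table 10. In the first gap case every value is Grade 2 or lower. The general clause in Section 5.2 permits withholding but does not require it. The pre-cycle chemistry review (Table 12, footnote n) states no liver value at which dosing must wait.

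**The case against.** The row logic is hard to dispute, but its weight can be. Table 10 is organised by parameter, so the maintain instruction answers the enzyme finding only. A reader might infer that the plan tells sites to dose through a Grade 2 bilirubin. It does not: it is silent on bilirubin in this corner. That point stands, but silence still leaves no required hold. Nor is the liver state always worse than at entry. A subject whose enzymes are unchanged at an assumed 4.0 × ULN, with only bilirubin new, also meets no row.

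Safeguards exist elsewhere. Section 4.10.1 requires discontinuation when the investigator judges the risk unacceptable. Section 5.2 calls for Medical Monitor consultation at the second occurrence of the same TEAE. Section 7.1.2.7 provides ongoing safety monitoring. These limit the consequence, but they rest on judgment or start after a first event.

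The state is also narrow. It needs abnormal baselines, both enzymes within the window, and bilirubin inside a band 0.5 × ULN wide, among at most 46 subjects. Dosing ends on Day 4, and the first post-dose chemistry listed for the run-in is Day 8 (Section 6.4.4). The two instructions therefore differ mainly at the next cycle. This stands and sets the size of the point.

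**Conclusion.** The gap is real on the printed text and independent of the contested readings. It is a minor safety correction. The documents give no patient frequency and none is claimed. The windows assume equal baselines for both enzymes and baseline equal to the entry value; the row at baseline 4.0 is illustrative.

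Two stronger conclusions are not supported.

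- **A gap at bilirubin ≥2.0 × ULN.** A reader might infer that the gap extends upward when another cause for the rise is found. That holds only if potential Hy's Law includes the no-other-cause condition. On the laboratory-threshold reading the footnote requires discontinuation, and the wording does not settle which is meant.
- **Bias in the DLT endpoint.** A dose reduction due to an AE is a DLT under Section 5.1.3, so a reader might infer that escalation decisions are distorted. The difference arises at a first occurrence only when resolution takes more than 7 days. At 50 mg/day no lower level is printed, and the Data Review Team may designate other toxicities as DLTs. No material effect is shown.

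**What to change.** 1. In Table 10, delete the ALT/AST condition from the Grade 2 and Grade 3 bilirubin rows, so that they apply whatever the enzymes are.
2. Leave the Hy's Law footnote unchanged.
3. Add one sentence: if more than one row applies, follow the strictest instruction. This is needed because the example subject would then meet both omit and maintain.

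After the change the bilirubin rows cover >1.5 to 3.0, >3.0 to 10.0 and >10.0 × ULN with no enzyme condition. Every bilirubin above 1.5 × ULN then meets a row that requires omission, evaluation for discontinuation, or discontinuation, and none is left with no row or only maintain.

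Deleting the condition is safer than narrowing it. A version limited to both enzymes <3.0 × ULN or bilirubin <2.0 × ULN would drop the bilirubin row where it now literally applies, for example at ALT 3.5, AST 1.0 and bilirubin 2.5 × ULN.

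The cost is a rewording of one table and a few extra dose holds. No tests or subjects are added.

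### Table 10's cell for a first Grade 3 bilirubin event is incomplete however its sign is read, and the evaluation triggers there and for AST/ALT appear reversed

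*Combined protocol and SAP*

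**What the plan says.** Section 5.2 directs sites to Table 10 for every hepatic event, and the footnote to Table 3 hands hepatic events over to it. Four sets of cells matter.

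- **Grade 3 bilirubin, first occurrence (Table 10).** After the dose is withheld until recovery, the first branch is "If resolved in ≤7 days, ↓ 1 dose level"; return to the original dose may be considered later, after consultation with the Medical Monitor, if nothing recurs. A sentence with no time condition follows: "Omit dose until resolved to ≤Grade 1, then: ↓ 1 dose level". Then comes "If not resolved or resolved in ≤7 days, evaluate if other contributing factors are present". APR-548 is stopped if no such factor is found or on a best-interest judgement, and the cell ends there.
- **Grade 3 AST/ALT, first occurrence (Table 10).** Recovery within 7 days, day 7 included, keeps the dose. The next sentence reads "If not resolved or resolved in $< 7$ days, evaluate if other contributing factors are present". This cell goes on to cover both the case where a factor is found and the case where the dose cannot be reduced.
- **Grade 2 bilirubin and Grade 2 AST/ALT, first occurrence (Table 10).** Recovery within 7 days keeps the dose, and slower recovery has its own branch: "If resolved in >7 days, then ↓ 1 dose level".
- **Grade 3 creatinine, first occurrence (Table 9).** The evaluation applies to events that are unresolved or took more than 7 days to resolve.

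**The concern.** A dose-modification table should send each event to one action. The Grade 3 bilirubin cell does not, for two separate reasons. Some of its instructions are missing or unattached, and its evaluation trigger, like the one for AST/ALT, points at the fast-recovering events that the preceding branch has already dealt with.

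At stake is whether sites treat like subjects alike. In a first-in-human study at up to 10 centers, one site could reduce or maintain the dose after a quickly resolving Grade 3 liver event while another opens an evaluation that may end treatment.

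**Working it through.** No sample size or error rate is involved. The check sets the cells side by side and follows each possible event through them.

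**Step 1: gaps in the Grade 3 bilirubin first-occurrence cell that do not depend on the sign**

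1. *Unattached sentence.* "Omit dose until resolved to ≤Grade 1, then: ↓ 1 dose level" carries no time condition and is tied to neither branch.
2. *No action if a factor is found.* Five cells call for an evaluation of contributing factors: Grade 3 creatinine first occurrence in Table 9, and the first- and second-occurrence Grade 3 cells for bilirubin and for AST/ALT in Table 10 (1 + 4 = 5). Four name an action when factors are found, for example "If other factors present, consider continuing after ↓ 1 dose level" in the bilirubin second-occurrence cell. The bilirubin first-occurrence cell is the exception (5 − 4 = 1).
3. *No fallback if the dose cannot go down.* Eight Table 10 cells include a one-level reduction: two parameters × Grades 2 and 3 × first and second occurrence = 8. Seven say what to do if that is impossible, typically "If unable to reduce by 1 dose level, then consult with study Medical Monitor". The same bilirubin cell is the exception (8 − 7 = 1).

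Gap 3 applies at the starting dose. The preliminary levels are 50, 150, 300 and 450 mg/day, so the one-level reductions are:

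- 450 to 300 mg: (450 − 300)/450 = 33%
- 300 to 150 mg: (300 − 150)/300 = 50%
- 150 to 50 mg: (150 − 50)/150 = 67%
- 50 mg: no lower planned level

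**Step 2: branches by day of resolution, with the signs as they read in the available text**

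| First-occurrence cell | Day 5 | Day 7 | Day 10 |
|---|---|---|---|
| Grade 2 bilirubin | maintain | maintain | reduce |
| Grade 2 AST/ALT | maintain | maintain | reduce |
| Grade 3 creatinine | reduce | no branch | evaluate |
| Grade 3 bilirubin | reduce and evaluate | reduce and evaluate | no timed branch |
| Grade 3 AST/ALT | maintain and evaluate | maintain | no timed branch |

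Two of the five cells that branch on 7 days overlap. The AST/ALT overlap excludes day 7 itself. An event resolving on day 10 could be sent to evaluation by treating it as unresolved at day 7, but neither cell says so; in the bilirubin cell the unattached sentence could also be applied to it.

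Example at 300 mg/day with recovery on day 5:

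- *Bilirubin:* 150 mg under the first branch. Under the second, evaluation, then 0 mg if no factor is found and no stated dose if one is.
- *AST/ALT:* 300 mg under the first branch. Under the second, evaluation, then 0 mg if no factor is found, or continuation at 150 mg to be considered if one is.

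**Step 3: the same check with both evaluation triggers read as more than 7 days**

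| First-occurrence cell | Day 5 | Day 7 | Day 10 |
|---|---|---|---|
| Grade 3 bilirubin | reduce | reduce | evaluate |
| Grade 3 AST/ALT | maintain | maintain | evaluate |

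No cell overlaps (0 of 5), and the AST/ALT cell becomes complete. The bilirubin cell keeps all three gaps from Step 1.

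**The case against.** The strongest reply is that the overlap rests on two characters. They come from text extracted from a PDF, and a misread sign is not a fault in the plan. The intended reading is also clear: the re-escalation clause for fast-recovering bilirubin events makes sense only if those subjects stay on drug, and Table 9 and both Grade 2 rows treat slow recovery more strictly than fast. This stands, and it is why the overlap is stated conditionally. It does not reach the three gaps in Step 1.

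A second reply is that the gaps nearly close themselves. The unattached sentence could be the default when a factor is found, and consulting the Medical Monitor when no reduction is possible is usual elsewhere in these tables. Both are reasonable guesses, but the cell states neither. Table 9's footnote on unavailable reductions belongs to Table 9. Table 3 has a fallback, but its footnote sends hepatic events away.

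A third reply is that the Medical Monitor prevents harm. Section 5.2 asks for consultation before permanent discontinuation. That sentence follows a rule on events unresolved at about 4 weeks, but it can be read as covering any permanent stop. Section 7.1.2.7 makes the Medical Monitor available to sites, and APR-548 is given only on Days 1 to 4 of each 28-day cycle. These points lower the severity. None says which branch governs an event that has already resolved.

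A reader might infer that the table requires stopping APR-548 in subjects who recover quickly. It does not: the second branch requires an evaluation, and stopping depends on its result or on a best-interest judgement.

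**Conclusion.** The point holds in two parts of different strength. The Grade 3 bilirubin first-occurrence cell has three defects under any sign: an unattached sentence, no action when another factor is found, and no fallback when the dose cannot be reduced. The reversed triggers for bilirubin and AST/ALT are a defect only if the signs match the source PDF; if both prove to be more than 7 days, the overlap disappears and the AST/ALT cell needs no change.

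A reader might also infer that DLT counts or escalation are at risk. The documents do not support that. Under Section 5.1.3 a non-hematological event of Grade 3 or higher already qualifies as a DLT by grade in both run-in windows, whichever dosing branch is then followed. The effect is confined to consistent dosing of individual subjects across sites. Nothing in the documents shows how often the cell would apply. Severity is minor to moderate.

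**What to change.** 1. Check the two signs against the source PDF.
2. In both Grade 3 first-occurrence cells of Table 10, keep recovery within 7 days (day 7 included) for the first branch. Let the evaluation apply to events that are unresolved or took more than 7 days. Take only the trigger from the Table 9 creatinine cell, because its first branch stops short of day 7 and leaves that day uncovered.
3. In the bilirubin cell, delete the untimed reduction sentence or assign it to one branch.
4. In the same cell, add "If other factors present, consider continuing after ↓ 1 dose level" and "If unable to reduce by 1 dose level, then consult with study Medical Monitor", the latter with the ending used in the sister cells (before treatment is resumed or stopped).
5. Have the clinical team confirm the intended actions.

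The cost is protocol wording: up to two triggers, one sentence removed or placed, and two sentences added to one cell. Design, sample size and analysis do not change.
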